Data to be collected will consist of maternal age and ethnicity, gravida/para, gestational age, height, weight, estimated fetal weight, reason for induction, date and time of device placement, date and time of delivery, mode of delivery, Bishop score at eligibility assessment, Bishop score prior to dilator insertion, Bishop score after removal or expulsion of dilator, date and time of rupture of membranes, date and time of device expulsion/removal, hospital length of stay, other intrapartum and obstetrical interventions, complications in device placement and cervical ripening, during labor and delivery including but not limited to meconium, infections, hemorrhage, fetal decelerations and subject satisfaction. We will also collect the amount of analgesics subjects received during device placement, cervical ripening and induction time (includes acetaminophen or intravenous medications or regional anesthesia). Data will be abstracted from the medical records as well as from direct interview. We will also collect basic neonatal data including birth weight, Apgar scores, rate of admission to neonatal intensive care unit, infections, and other neonatal complications. The data collected will not be used for clinical diagnosis or treatment purposes. Additional economic data to be collected includes the following admission direct costs or charges from the following services/departments: Blood Bank Transfusion Operations, Chemistry Division, Hematopathology Division, JSH Labor & Delivery unit, Materials Management, Microbiology Division, Mother Baby Unit, Pharmacy, Respiratory Care Services, Surgical Operating Suite.

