### **5.3. Randomization**

After Dilapan-S® placement, and if the subject remains eligible, subject will be randomized to the outpatient group or the inpatient group. A confidential computer-generated simple randomization scheme will be prepared and provided by independent vendor (PharmTest, s.r.o., Czech Republic) to our study coordinator. The currently used randomization code will be replaced by 2 randomization codes, 1 of them for CUMC site (both clinics will use the same randomization sequence. The randomization envelopes to be used at CUMC will be provided by UTMB).

A randomization log with group assignment, subject name, and medical record *number* will be used to track the randomization process. The subject will be included in the analysis by intent-to-treat once the randomization assignment has been made.

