### **5.4. Pre-Induction**

#### **5.4.1. Group Assigned to Outpatient Cervical Ripening**

After Dilapan-S® placement, subject will be monitored for at least 30 minutes. If no contraindications, such as tachysystole, active vaginal bleeding, rupture of membranes or nonreassuring fetal testing (defined as minimal or absent variability, abnormal baseline, or presence of decelerations) evidence of labor, or other serious medical conditions deemed by the clinical staff or the attending physician to preclude outpatient cervical ripening develop after insertion, the subjects will be randomized. After randomization subject will record the pain she experienced during insertion in the patient's survey (see Appendix 3). Those subjects randomized to outpatient ripening will be given the option to either stay in a hotel or, if they are able to reach the hospital within 60 minutes, return home. The cost for the hotel will be covered by the study budget. Subjects at CUMC will solely be given the option to stay at home. Subjects will be allowed to ambulate, shower and perform regular activity during that period. "Nothing per vagina" will be allowed (incl. intercourse, tampons etc.). Subjects will also be instructed to return to L&D unit 12 hours after insertion, or earlier if any excessive bleeding, rupture of membranes, pain or other concerns (contractions, decreased fetal movement) develop before the 12 hours. Special leaflet (Appendix 2) will be provided to subjects leaving the hospital, with detailed instruction, emergency contacts to appropriate study/clinical staff and space to document of oral medication taken for pain relief (acetaminophen). Subject will also document the date and time of membrane rupture if applicable.

Reasons for examining or removing dilators earlier include but are not limited to:

- 1) Spontaneous onset of labor  
(defined as regular, firm, uterine contractions with an effaced cervix >80% and a cervical dilatation > 3 cm)
- 2) Other than category I fetal heart rate tracing  
(category I includes all: Baseline rate: 110–160 beats per minute, baseline FHR variability: moderate, absent late or variable decelerations, Early decelerations: present or absent and accelerations: present or absent)
- 3) Spontaneous rupture of membranes or need for amniotomy
- 4) Spontaneous expulsion of Dilapan-S® rods
- 5) Subject removed the rods herself

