## **13. Biostatistics/Sample Size**

Basic principles for an evaluation of the study are presented in this section, more detailed description of how to analyze collected data will be specified in statistical analysis plan (SAP) which will be written and approved before the database lock. The statistical analysis including the data from the additional site will be specified in the SAP.

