#### *Intent-to-treat Population (ITT)*

ITT includes all patients that were randomized into the study and primary outcome has been obtained. ITT subjects will be analyzed in accordance with their randomized study treatment (i.e. in the treatment group they were originally allocated, regardless of treatment actually received). ITT will be used for evaluation of the baseline characteristics and as the primary population for efficacy assessments. Other predefined subgroup interaction analysis for cervical dilation at randomization, parity ( $P=0$  vs  $P>0$ ), or  $BMI > 30 \text{ kg/m}^2$  will be also performed.

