### **13.2. Analysis of primary outcome**

Primary outcome of the study is the rate of hospital stay longer than 48 hours. Proportion of patients in the outpatient and inpatient group will be calculated and their difference will be tested by chi-square test by ITT analysis.

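### The primary test in section 13.2 is an unadjusted chi-square; stratifying it by parity, already collected, would add up to about 2.3 points of power at almost no cost

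*Combined protocol and SAP*

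**What the plan says.** - **Primary test.** Section 13.2 calculates the proportion with a stay over 48 hours in each arm, and "their difference will be tested by chi-square test by ITT analysis". No covariate or stratum is named. Section 13.3 treats nominal secondary outcomes the same way.
- **Parity as data.** Section 3 lists it at baseline: "Data to be collected will consist of maternal age and ethnicity, gravida/para, gestational age". The ITT paragraph of section 13.1 splits it into 0 versus more than 0, but only for interaction analysis: "Other predefined subgroup interaction analysis for cervical dilation at randomization, parity".
- **Randomisation.** Section 5.3: "A confidential computer-generated simple randomization scheme will be prepared". It adds that "The currently used randomization code will be replaced by 2 randomization codes", one of them for CUMC. Parity is not a stratification factor.
- **Further detail.** Section 13 gives basic principles and leaves the rest to a SAP "which will be written and approved before the database lock". On site: "The statistical analysis including the data from the additional site will be specified in the SAP". That SAP is not part of the supplied text.
- **Planning figures.** Section 13.4 assumes 54% versus 37.8%, 85% power and two-sided alpha of 0.05. It arrives at 169 per group, then 188 per group and 376 in total after 10% dropout.

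**The concern.** With a binary endpoint and simple randomisation, a baseline factor that predicts the outcome does two things to a crude comparison. It adds between-woman variation that a stratified analysis would remove, and any chance imbalance in it moves the estimate. If parity predicts a stay over 48 hours, a test stratified by parity has more power at the same sample size and type I error. If it does not, almost nothing is lost. The documents do not say whether parity is prognostic.

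The deadline also matters. Database lock is late for settling a primary test in this trial. Staff can see the arm: section 5.4.1 says "Those subjects randomized to outpatient ripening will be given the option to either stay in a hotel" or, if they can reach the hospital in time, go home, while section 5.4.2 admits the inpatient arm to the labour unit. Section 5.3 refers to a randomisation code already in use. Under section 5.5 the investigators themselves review and validate outcomes. A choice of test is most credible if it is dated before any outcome has been looked at by arm.

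**Working it through.** **1. Reproduce the plan's sample size.** Inputs from section 13.4: p1 = 0.54, p2 = 0.378, difference d = 0.162, mean rate 0.459.

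n = [1.960·√(2·0.459·0.541) + 1.036·√(0.54·0.46 + 0.378·0.622)]² / 0.162²
= [1.3812 + 0.7207]² / 0.026244 = 168.4, so **169 per group**.

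Then 169/0.90 = 187.8, so 188 per group and 376 in total. All three figures agree with the plan. Crude power at 169 per group is Φ[(0.162·√169 − 1.960·√0.4966)/√0.4835] = Φ(1.042) = **85.1%**.

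**2. Assumptions the documents do not supply.** The nulliparous share is taken as 40-60%. The parity OR for a stay over 48 hours runs from 1 to 5 and is the same in both arms. Overall rates are held at 54% and 37.8%, with 338 evaluable women (2 × 169). At 50% nulliparous, the implied control-arm rates (nulliparous versus parous) are 62.5% versus 45.5% at OR 2, 67% versus 41% at OR 3 and 73% versus 35% at OR 5. OR 5 is therefore a very strong effect.

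**3. Approximate check at OR 3, 50% nulliparous.** Solving for the marginal rates gives 0.673 and 0.407 (inpatient) and 0.503 and 0.253 (outpatient). The crude variance terms 0.4966 (null) and 0.4835 (alternative) become averages over the two strata:

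- null: ½[2·0.588·0.412 + 2·0.330·0.670] = 0.463
- alternative: ½[(0.673·0.327 + 0.503·0.497) + (0.407·0.593 + 0.253·0.747)] = 0.450

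Power = Φ[(0.162·13 − 1.960·√0.463)/√0.450] = Φ(1.15) = **87.5%**, against 85.1% crude: a gain of 2.4 points.

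**4. Simulation.** 200,000 trials per scenario, simple 1:1 randomisation (so arm sizes vary), no continuity correction. Ranges cover 40-60% nulliparous.

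| Parity OR | Chi-square power (%) | Parity-stratified CMH power (%) | Change (points) |
|---|---|---|---|
| 1 | 84.9-85.2 | 84.8-85.1 | -0.13 to -0.16 |
| 1.5 | 85.0-85.1 | 85.2-85.3 | +0.2 |
| 2 | 85.1 | 85.9-86.0 | +0.8 to +0.9 |
| 3 | 85.0 | 87.2-87.3 | +2.2 to +2.3 |
| 5 | 85.0-85.1 | 89.4-89.7 | +4.4 to +4.7 |

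Type I error: chi-square 4.84-5.13%, CMH 4.84-5.09%. Both methods estimate -16.2 points on average. The SD of the estimated difference is 5.35-5.37 points crude, and stratified it is 5.28-5.29 (OR 2), 5.18-5.19 (OR 3) and 4.98-5.00 (OR 5).

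**5. The gain in women.** Crude power is 85.1% at 169 per group, 87.3% at 180 and 89.7% at 195. To match the stratified test, the chi-square would need about 8 more evaluable women at OR 2, 22 at OR 3 (2 × 11) and 48-52 at OR 5.

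**6. Chance imbalance.** The SD of the between-arm difference in nulliparous share is √(p(1−p)·2/169): 5.33 points at p = 0.4 or 0.6, and 5.44 at p = 0.5. An imbalance above 10 points therefore occurs in 6.1-6.6% of trials. It would move the crude difference by about 10% of the parity risk difference, that is 1.7 points at OR 2 and 2.6 at OR 3, against a planned effect of 16.2. This does not bias the test over repeated trials, but it affects the estimate in the trial at hand.

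**The case against.** **Nothing is broken.** The chi-square is valid, matches the sample-size formula and meets the design power. That stands, and it is why this is only a suggestion.

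**The benefit is assumed.** No document says that parity predicts a stay over 48 hours, and section 13.1 lists parity beside cervical dilation and BMI without singling it out. This also stands. The gain is a range that starts slightly below zero.

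**The loss could be larger.** With arms of exactly 169 each, simulation gives about -0.6 point at OR 1, +0.2 to +0.4 at OR 2 and +1.4 to +1.8 at OR 3 (30-60% nulliparous). Much of that gap arises because the uncorrected chi-square then rejects a true null about 5.2% of the time, against 5.0% for CMH. Section 5.3 specifies simple randomisation, under which arm sizes vary and the excess disappears.

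**Site is treated differently.** Site is left out of the proposed primary test partly because it adds less than 1 point at an assumed OR of 2, yet parity at OR 2 adds no more. As an argument from size, that objection is fair. Two reasons remain: section 13 already assigns site to the SAP, and if CUMC contributed 10% of women, some parity-by-site-by-arm cell would hold fewer than 5 women in 27-39% of trials. At a 30% share this problem vanishes.

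**It may be too late.** Appendix 1 carries an April 2021 revision of the instructions for use, and section 3 ends the study period in December 2021. Replacing a named primary test at that stage, with arms visible to staff, has a credibility cost. This is the strongest point, and it is why the change depends on nobody having examined outcomes by arm.

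**The SAP may already cover it.** That cannot be judged from the supplied text. If it does, only section 13.2 needs aligning.

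**Conclusion.** The point holds as an optional efficiency gain. The planned chi-square is sound and keeps its 85% power. Under the documented simple randomisation, a parity-stratified test changes power by about -0.15 point at a parity OR of 1, +0.8 to +0.9 at 2 and +2.2 to +2.3 at 3, with type I error unchanged at about 5%. Larger gains need a very strong parity effect. The size rests entirely on an assumed parity OR and an assumed 40-60% nulliparous share. Confidence is moderate: the arithmetic is secure, but the prognostic strength of parity is unknown from the documents. With full retention at 188 per group, crude power is already 88.6%, and the approximate gain at OR 3 falls to 1.6-2.1 points.

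**What to change.** 1. In section 13.2 and the SAP, name a Cochran-Mantel-Haenszel test stratified by parity (0 versus more than 0) as the primary test, with the Mantel-Haenszel risk difference and its 95% CI. Keep the unadjusted chi-square as a sensitivity analysis.
2. Date this before any outcome is examined by arm, not merely before database lock. If outcomes by arm have already been seen, leave the chi-square as primary and report the parity-stratified result as the sensitivity analysis.
3. Leave site to the SAP, for example as a sensitivity analysis stratified by parity and site.
4. State whether parity stratification also applies to the nominal secondary outcomes in section 13.3.

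**Cost.** A wording change with no new data. The statistical price if parity is unrelated to stay is 0.13-0.16 point of power under simple randomisation, or about 0.6 point if the arms happened to be exactly equal. A late change also has to be justified openly, which is the purpose of the condition in item 2.

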**Randomization** will be performed using a computer-generated random list of numbers assigning subjects to the 2 groups of the study. This list of random number assignments will be kept secure in an opaque envelope until the end of the study. 2 randomization sequences will be required for UTMB and CUMC sites.

No significant adverse effects are expected with the use of Dilapan-S® for mechanical dilation as an outpatient when compared to inpatient setting. The most common adverse events from cervical ripening with mechanical dilators such as the Foley balloon have been reported to be less than 1% (8), the most common being pain (0.26%), unintended amniotomy (0.04%), vaginal bleeding (0.07%), non-reassuring fetal heart tracing (0.07%), and uterine tachysystole (too low to quantify). Our group also reported the following adverse effects with inpatient use of Dilapan-S® for cervical ripening in a group of 444 subjects (9):

Maternal and neonatal adverse events	Nr. of cases (%)	Comments (n)
Uterine tachysystole	1 (0.2)	
Non reassuring fetal heart rate	1 (0.2)	
Maternal complications/discomfort	15 (3.4)	Bleeding during insertion/extraction of dilators (12), Cramping/pain (1), Other (1)
Uterine contractions	111 (25)	Tocography during cervical ripening showed low frequency and mild intensity contractions
Maternal infection	14 (3.2)	Chorioamnionitis (9), Urinary tract infection (3), Endomyometritis (1), Wound infection (1)

NICU admission	6 (1.4)	Meconium aspiration (2), Growth restriction (2), Asphyxia (1), Congenital cardiac abnormality (1)
Neonatal infection	1 (0.2)	Neonatal sepsis (maternal group B Streptococcus was not observed prior IOL)

The most significant potential risks noted with Dilapan-S® occur during or shortly after insertion and include vaginal bleeding due to cervical trauma and incidental rupture of membranes, as well as pain or discomfort with placement. If these occur and are persistent (i.e. unresolved pain despite analgesia), subjects will be admitted for delivery (as they require maternal monitoring) and will not be randomized, since they do not fulfill the eligibility criteria to receive the outpatient intervention.

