## **6. Study Outcomes**

### **6.1. Primary Outcomes**

Rate of hospital stay longer than 48 hours (from admission to discharge)

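### Women are allocated from separate UTMB and CUMC sequences, but the only primary test stated has no site term; stratifying it by site would be a small, nearly free gain

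*Combined protocol and SAP*

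**What the plan says.** - **Allocation.** Section 3 states that "2 randomization sequences will be required for UTMB and CUMC sites". Section 5.3 describes "A confidential computer-generated simple randomization scheme" and adds: "The currently used randomization code will be replaced by 2 randomization codes, 1 of them for CUMC site". The CUMC clinics share one sequence. No blocking is described.
- **Intervention.** Under Section 5.4.1, women in the outpatient arm are "given the option to either stay in a hotel or, if they are able to reach the hospital within 60 minutes, return home". For the second site the rule is narrower: "Subjects at CUMC will solely be given the option to stay at home".
- **Primary test.** The outcome is a hospital stay above 48 hours. Section 13.2 compares the two proportions, and "their difference will be tested by chi-square test by ITT analysis". It names no site term, effect estimate or confidence interval. Section 13.3 carries the same test to nominal secondary outcomes and uses the log-rank test for times to event.
- **Subgroups.** Section 13.1 lists cervical dilation, parity and BMI for interaction analyses. Site is not listed.
- **Deferral.** Section 13 presents itself as an outline and says: "The statistical analysis including the data from the additional site will be specified in the SAP". That SAP is due by database lock.
- **Planning rate.** Section 13.4 takes 54% in the control arm from UTMB experience and a registry. It gives no CUMC figure and no expected CUMC share.

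**The concern.** Site defines how women are allocated, and a stay beyond 48 hours plausibly depends on local discharge practice. If the sites differ, a test with no site term leaves that difference in the residual variation and gives up some power. Under simple randomization nothing forces the arms to balance within a site, so the site mix can also differ between arms by chance.

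Timing is a second reason to settle the matter. The arms cannot be masked from site staff, and the SAP may be approved as late as database lock. Leaving the choice between an adjusted and an unadjusted primary test until then is flexibility the trial does not need.

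A different question arises from the outpatient arm. Its content differs by site, so the effect may differ too, and no predefined analysis would show this.

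**Working it through.** **1. The plan's own figure.** Inputs from Section 13.4: 0.54 and 0.378, two-sided alpha 0.05, power 85%. The mean rate is 0.459.

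n = [1.96 × √(2 × 0.459 × 0.541) + 1.036 × √(0.54 × 0.46 + 0.378 × 0.622)]² / 0.162² = (1.381 + 0.721)² / 0.02624 ≈ 168.4, so 169 per group. Then 169 / 0.9 = 187.8, so 188 per group and 376 in total. The stated figures reproduce.

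**2. Stratified against unstratified test.** Assumptions, because the plan gives neither quantity: CUMC share f of 20-50%, and a gap g between the sites' control rates of 0 to 30 points in either direction. The overall control rate is held at 0.54, so UTMB has 0.54 − f·g and CUMC has that plus g. Allocation is simple 1:1 within site, with 2 × 169 = 338 evaluable women.

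For each site, with n women, a of them outpatient, m events and x outpatient events, the CMH statistic is [Σ(x − a·m/n)]² / Σ[a(n − a)m(n − m) / (n²(n − 1))].

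Example with f = 0.35 and g = 0.20: the control rates are 0.47 and 0.67, and the outpatient rates under a common odds ratio are 0.309 and 0.506. Simulated power is 85.0% for chi-square and 86.15% for CMH, a gain of 1.15 points.

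| Gap in control rate | Chi-square power | CMH change, common odds ratio | CMH change, common risk ratio 0.7 |
|---|---|---|---|
| 0 | about 85% | −0.1 to −0.2 | about −0.2 |
| 10 points | about 85% | +0.1 to +0.3 | about neutral |
| 20 points | about 85% | +0.6 to +1.2 | +0.5 to +1.0 |
| 30 points | about 85% | +1.6 to +3.0 | +1.3 to +2.3 |

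Type I error was 0.049-0.051 for both tests in every common-odds-ratio scenario. With all 376 women the gains at 20 and 30 points are 0.6-1.1 and 1.5-2.6.

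The gains are small because site explains little of the variance. With a 50/50 split and a 20-point gap, its share is 0.25 × 0.2² / (0.459 × 0.541) = 4%. At 10 and 30 points it is 1% and 9%.

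**3. Chance imbalance in site mix.** The SD of the between-arm difference in CUMC share is √(4f(1 − f)/338): 4.4 points at f = 0.2 and 5.4 at f = 0.5. At a 20-point gap the 95% range of the resulting shift is 1.96 × SD × 0.20, or 1.7 to 2.1 points. For comparison, the standard error of the planned difference is √[(0.2484 + 0.2351)/169] = 5.35 points, a 95% half-width of 10.5.

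**4. A different effect by site.** Suppose the CUMC effect is half of 16.2 points, that is 8.1. The overall outpatient rate becomes 0.378 + 0.081f, and pooled power at 169 per group is 77%, 69% and 61% for CUMC shares of 20%, 35% and 50%.

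A test for that interaction has SE √{0.4835 × [1/(169f) + 1/(169(1 − f))]}, which is 13.4 points at f = 0.2 and 10.7 at f = 0.5. The ratios 8.1/13.4 = 0.61 and 8.1/10.7 = 0.76 give power of about 9% and 12%.

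**The case against.** The strongest reply is that Section 13 assigns exactly this matter to the SAP. That stands as far as it goes. A reader might infer that the trial's final primary analysis ignores site; the document does not show this. It shows only that Section 13.2 names no site method and that the method is left to a later text.

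Three further inferences are tempting and do not hold.

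- **That separate sequences make the pooled test invalid.** Omitting a stratum distorts the test's level when allocation is balanced within strata. Here it is simple, so two 1:1 sequences behave like one, and the chi-square keeps its level without bias.
- **That chance site imbalance is an extra threat.** The shift of 1.7-2.1 points is a component of sampling error already inside the 10.5-point half-width.
- **That hotel or home against home only is noise which stratification removes.** It is a difference in the intervention. CMH does not recover power lost to a weaker effect at one site. Nor does site isolate home-only care, because UTMB women within 60 minutes may also go home.

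The assumed gaps also have limits. At an equal split, a 30-point gap puts the UTMB control rate at 39% or 69%, which fits poorly with a 54% rate drawn partly from UTMB experience. The top of the range is therefore less plausible than the middle.

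What survives is modest: naming a test that follows the allocation costs almost nothing, and doing so now removes a late choice.

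**Conclusion.** The point holds as a minor one. The stated primary test does not use the site structure of the allocation, and the document supplied does not yet say how the two sites will be combined. The possible loss is precision only, somewhere between a 0.2-point advantage for the unstratified test and about 3 power points against it. For site gaps up to 20 points it is roughly one point or less.

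These figures rest on an assumed CUMC share of 20-50%, assumed control-rate gaps of up to 30 points, and a treatment effect constant across sites on the odds-ratio or risk-ratio scale. The document gives no length of stay by site, so a site difference is itself an assumption.

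The possible difference in effect between sites is a separate matter of interpretation. It could cost more than the missing site term, but the halved CUMC effect used above is an illustration and not something the document suggests.

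**What to change.** - **Section 13.2:** make the primary test a CMH test stratified by site (UTMB, CUMC). Report a site-adjusted risk difference with its 95% confidence interval, described as a weighted average, since risk differences need not be equal across sites. Keep the unstratified chi-square as supportive.
- **Section 13.3:** stratify the secondary binary comparisons and the log-rank tests by site in the same way.
- **Section 13.1:** add the effect by site as a predefined descriptive analysis. Note its low power and that site is not a clean contrast of home-only care.
- **Earlier code:** Section 5.3 replaces a code already in use, so state which stratum holds the women randomized under it.
- **SAP:** carry the same wording there, and fix it well before database lock.

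The cost is short edits to Sections 13.1 to 13.3 and about 0.2 power points if the sites do not differ. No more women are needed.
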